Study Title: An investigation into the feasibility of incorporating an exercise rehabilitation programme for people with intermittent claudication into an already established Cardiac Rehabilitation service

Protocol

Overview

This study will look at the feasibility of combining patients with peripheral artery disease (PAD) and coronary artery disease (CAD) into one supervised exercise programme (SEP). The study will assess the effects of the intervention quantitatively, and also investigate the patient experience qualitatively by applying a mixed methods design (figure 1). The initial phase of the research will quantitatively analyse pre and post-intervention outcomes, followed by qualitative investigation into the thoughts and concerns about the intervention. The rationale for this mixed methods approach is that it provides strengths that offset the weaknesses of both qualitative and quantitative methods when used in isolation (Creswell & Plano Clarke, 2007). Also in clinical settings such as in the NHS, exploring the views and experiences of the service users to gain greater understanding has been shown to improve service provision and subsequently patient uptake (Risom et al., 2013).

[figure not shown]

Figure 1: This diagram shows the mixed methods approach of the research study, with the qualitative element following on from the quantitative measurement of the intervention outcomes. The results of each arm will be merged to show the overall effectiveness of the intervention.

Recruitment Strategy:

Intervention group:

Participants for the combined SEP will be recruited from a local NHS Vascular Service at Salford Royal NHS Foundation Trust (SRFT). They will be identified by the vascular specialist teams (surgeons, nurses and podiatrists) and asked if they wish to take part in the study. The participants will be asked during the face-to-face consultation with their specialist, or a telephone consultation. This will give participants 1-2 week period to consider enrolling in the research programme. Participation will be on a voluntary basis. Simultaneously, an agematched group of coronary artery disease (CAD) patients will be recruited to the combined programme to assess the impact of combined SEP on CAD patients. These participants will be identified by the Cardiac Rehabilitation Specialist Nurses at SRFT upon referral to the CR SEP and will have a similar 1-2 week period to decide about enrolling.

Control group or "standard care" group:

A control group will also be recruited. This group will be made of PAD patients only and will take place at an established SEP at Central Manchester University Hospitals. The use of a SEP has been chosen as the control group or "standard care" group, even though most patients are unable to receive the standard care in the UK. Other research in this area has had an "exercise advice only" group as control (Cheetham et al., 2004) however, it has been established that SEPs are better than "exercise advice only" as a treatment option (Bendermacher, Willigendal, Teijink and Prins, 2009). Therefore it would be unethical for some participants to be missing out on the recommended SEP treatment.

The CAD patient's outcomes will be compared to the National Audit of Cardiac Rehabilitation (NACR) as it is outside of the scope of this investigation to have a CAD only control group. The NACR data is compiled annually and records all of the outcome measures that are included in this study. The recent year's audit results will be used for comparison.

Informed Consent

In order to gain informed consent from prospective participants, the content and layout will verbally be given to prospective participants, along with an easy-to-read leaflet/letter with full description of the study (see Patient Information Sheet in supporting documents). To avoid any risk of coercion, it will be explicitly stated that they have the right to withdraw from the study at any point, and that no present or future treatment will be affected by enrolling or not enrolling on the study. All documents will be available in large print if required.

Sample size:

The sample size of this investigation has been guided by a study by Evans et al., (2010) which investigated the suitability of combining two different patient groups (heart failure and chronic obstructive pulmonary disorder) into one rehabilitation programme. The authors of this study established that 17 participants were required in each group to reach significance level.

There will be 3 participant groups in this study: The stand-alone PAD group; the combined PAD group, and the combined CR group (see figure 2). In order to generate sufficient data 34

patients will be recruited to each group with an aim to achieve 17 completers from each group. This is due to an expectation of high dropout rate for both PAD and CAD programmes seen at a national level (NACR, 2016; Shalhoub et al., 2009). The total recruited will therefore be 102 subjects, to gain 51 completers totally (17 per group).

[figure not shown]

Figure 2 - Flowchart of study. This shows the outline of the 12 week study with the 3 groups involved

Inclusion and Exclusion Criteria

General criteria

As part of this study participants will be required to wear an accelerometer on the first week and last week of the 12 week study. The accelerometer will be kept in place by a medical dressing (e.g. Tegederm). People with an existing skin condition such as psoriasis or eczema that would be affected by the application of a medical dressing will be excluded from the study.

All participants must be able to start the incremental shuttle walk test (walking speed of 1.8kph, 1.1 mph). If they are unable to walk at this pace they will be excluded from the study.

All participants must be able to engage in the exercises prescribed in the programme (see Supervised Exercise Programme outline below).

No participant will be excluded due to age or gender.

Inclusion Criteria – PAD patients:

All patients recruited will have had a recent diagnosis (0 – 12 months) of PAD made by either a vascular surgeon, vascular specialist nurse or specialist podiatrist.

Exclusion criteria – PAD patients:

Any patient who has had previous intervention for PAD e.g. balloon angioplasty, stent, bypass or medication, or who have previously completed an SEP will be excluded from the study. This is due to the possibility of previous interventions having an impact on patient perceptions.

Participants who are on medication for PAD (e.g. naftidrofuryl oxalate) will also be excluded from the study as this can increase symptom management and improve functional capacity.

Any PAD patient who also has a diagnosis of other cardiovascular conditions such as CAD or stroke, or chronic heart failure will be excluded from this study, as the investigation is looking at the specific improvements in PAD, not CAD gains.

Inclusion Criteria – CAD patients:

All patients recruited to the CR group will have had a recent diagnosis (0-12 months) of CAD (angina, myocardial infarction (MI), or coronary artery bypass graft (CABG) or valve surgery).

Exclusion criteria – CAD patients:

Any patient who has had previous diagnosis of PAD will be excluded from the study, as this may mask any gains in improvement due to CAD-specific rehabilitation in the CAD group (Tam et al., 2016).

Any participant who has unstable CAD (e.g. unstable angina) will be excluded from the study as this is a contraindication partaking in structured exercise programme (BACPR, 2012).

Study Design

Initial Assessment

All participants will be fully assessed prior to starting their 12 week SEP. This assessment is a standard part of the SEP process where a range of standard clinical measures are recorded (e.g. resting BP, BMI, and waist circumference). This will be conducted by one of the rehabilitation team members. All outcome measures will be taken prior to the patients starting their SEP and repeated upon completion of the programme. A summary of all outcome measures is shown in table 1. Completion will be categorised as attending 8 or more of their 12 sessions.

Quantities subjected to post hoc analysis		
Quantity	Time of measure (weeks)	
Demographic		
Sex (M/F)	BL	
Age (years)	BL	
Clinical		
Blood Pressure (mmHg)	BL, 12 weeks	
Resting Heart rate (bpm)	BL, 12 weeks	
Height (m), weight (kg), BMI (kg.m²)	BL, 12 weeks	
Waist circumference (cm)	BL, 12 weeks	
Medication	BL, 12 weeks	
Physical Functioning		
Incremental Shuttle Walk Test (ISWT)	BL, 12 weeks	
7-day activity monitoring	BL, 12 weeks	
Questionnaires		
VascuQol (PAD only group)	BL, 12 weeks	
Hospital Anxiety and Depression Scale (HADS)	BL, 12 weeks	
Walking Impairment Questionnaire (WIQ)	BL, 12 weeks	
BL, Baseline; PAD, peripheral artery disease		

Table 1 – This table provides a summary of quantitative outcome measures and the time-point at which they will be recorded

Outcome measures:

The following items are the outcome measures that will be recorded. The PAD-specific tests have been recommended by the TransAtlantic Inter-Society Consensus (TASC) Working Group for the Management of PAD (2007). The others are standard outcomes measures recommended by the British Association of Cardiovascular Prevention and Rehabilitation (BACPR).

- Incremental shuttle walk test (ISWT): This will assess walking distance, peak walking speed and functional capacity. For PAD patients it will also establish the pain-free and maximal walking distances. The ISWT is a functional exercise test (FET) that is commonly used throughout exercise rehabilitation programmes and research (Zwierska et al., 2005; Evans et al., 2010; ACPICR, 2015)
- Walking behaviour and physical activity will be recorded by an Activpal[®] accelerometer (as used in Clarke et al. 2012) to quantify free-living walking. It will be attached to the front of the thigh using a medical grade waterproof dressing. It weighs 15g so will not be a physical burden to the participants. It will remain in place on the leg for a seven-day period, prior to starting the SEP. This will show baseline activity, and during the last week prior to them completing their SEP.
- Quality of Life Measures
 - o Hospital Anxiety and Depression Scale (HADS) questionnaire
 - This is a 14-item questionnaire with 7 questions measuring anxiety and 7 questions measuring depression levels. This is a commonly used in clinical settings and is a standard questionnaire used in Cardiac Rehab departments (Coats et al, 1995; BACPR, 2012; ACPICR, 2015). It takes on average 5 minutes to complete this questionnaire.

- King's College Vascular Quality of Life (Vascu-QoL) Questionnaire (PAD-specific)
 - This is a 25-item questionnaire with 5 domains looking at disease-specific quality of life that has been widely used in PAD research (Morgan et al. 2001; Vries et al. 2005). Disease-specific quality of life measures are recommended by TASC (2007) in combination with generic questionnaires (such as HADs) as they are more sensitive to change in specific symptoms that are related to the condition. This questionnaire takes on average 10 minutes to complete.
- Walking Impairment Questionnaire (WIQ): This is a PAD disease-specific questionnaire assessing the perceived impact of claudication symptoms on the individual being measured. This is a commonly used questionnaire in PAD research since its development by Regesteiner et al. (1995), and is recommended by TASC (2007) to assess patient perceived symptoms. It takes on average 5 minutes to complete.

Supervised Exercise Programme Outline:

The Programme

Patients from all groups will attend a 2 hour supervised exercise session once a week, for 12-weeksEach session will start with a pre-screening interview to confirm suitability to exercise that day. The exercise will start with a 10-15 minute warm up, followed by a 20-25 minute conditioning phase, and a 10 minute cool-down. Successful completion of the programme will be achieved when 8 or more sessions are attended.

PAD specific exercise

The conditioning phase for the IC patients will involve completion of a range of exercises designed to bring on claudication within 3-4 minutes. Participants are encouraged to exercise to near-maximal claudication pain, and then rest until the pain has subsided before starting the next exercise. This is accordance with the AACVPR (2013) and NICE (2012) recommendations and will ensure safe and effective exercise. Monitoring and guidance will

be given throughout the exercise session by the rehabilitation team. The exercises will include:

- Treadmill walking
- Heel raises
- Trampette walking/jogging
- Sit to stands
- Corridor walking

CAD specific exercise

The conditioning phase for CAD patients will consist of a range of cardiovascular exercises designed to improve cardiovascular fitness. This will follow the standard cardiac rehabilitation programme guidelines set by the BACPR (2012) and Association of Chartered Physiotherapist working in Cardiac Rehabilitation (ACPICR) (2015).

Physical Activity and exercise advice:

As the programme of exercise is only once a week, the rehabilitation team will provide guidance and encouragement for patients to keep active outside of the sessions. Patients will be given pedometers to use and weekly activity goals will be set and reviewed each week by a member of the rehabilitation team to assess progression.

Patient education:

Following each exercise session all patients will be invited to attend education sessions. The sessions are based on the clinical guidance from NICE (2012) recommending patients are educated on the importance of lifestyle interventions including:

- aggressive lipid modification and statin therapy
- smoking cessation
- diet, weight management and exercise
- the prevention, diagnosis and management of diabetes
- the prevention, diagnosis and management of high blood pressure

antiplatelet therapy

Qualitative post-intervention study

Upon completion of the 12-week supervised exercise programme, participants will be invited to attend focus groups to explore their thoughts and concerns about the intervention (Figure 2). Themes will be constructed from the data to give insight into the experiences of the different participant groups. As participation is important for rehabilitation departments, it is essential to include the participants' perspective in the evaluation of the treatment programme.

Data Analysis:

Quantitative data:

The outcome data will be tested to see if it is normally distributed or not. SPSS software will then be used to assess for any statistically significant differences between the groups. Within groups and between group differences in exercise capacity will be analysed using a factorial ANOVA to compare the difference in the levels of improvement between groups. Wilcoxon tests will be used to analyse the questionnaire data.

The CAD group will also be compared to the National Audit of Cardiac Rehabilitation (NACR) data to assess the impact on the CAD group performance against expected national levels. The effect sizes will be calculated using the Cohen's *d* so that the results can be compared to other studies.

Qualitative Data:

The analysis will be influenced by Braun & Clarke's (2006) six phases of thematic analysis as described in Table 2.

Phase	Description of the process

1. Familiarizing yourself with your	Transcribing data (if necessary), reading and re-reading
data:	the data, noting down initial ideas.
2. Generating initial codes:	Coding interesting features of the data in a systematic
	fashion across the entire data set, collating data relevant
	to each code.
3. Searching for themes:	Collating codes into potential themes, gathering all data
	relevant to each potential theme.
4. Reviewing themes:	Checking if the themes work in relation to the coded
	extracts (Level 1) and the entire data set (Level 2),
	generating a thematic 'map' of the analysis.
5. Defining and naming themes:	Ongoing analysis to refine the specifics of each theme, and
	the overall story the analysis tells, generating clear
	definitions and names for each theme.
6. Producing the report:	The final opportunity for analysis. Selection of vivid,
	compelling extract examples, final analysis of selected
	extracts, relating back of the analysis to the research
	question and literature, producing a scholarly report of
	the analysis.

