The results of both the quantitative data analysis and the thematic analysis from the focus groups will then be used to draw conclusions about the effectiveness of the treatment options.

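### Programme and hospital coincide in the PAD comparison, so the planned test of improvement cannot support an unqualified conclusion about effectiveness

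*Protocol*

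**What the plan says.** The Protocol's Sample size section names three groups: "The stand-alone PAD group; the combined PAD group, and the combined CR group". Under Recruitment Strategy, the combined PAD patients are identified by the vascular teams at Salford Royal. The comparator is described in the control-group part of that section: "This group will be made of PAD patients only and will take place at an established SEP at Central Manchester University Hospitals". Allocation by chance is not mentioned in the text of either document; clinical teams identify patients and "Participation will be on a voluntary basis". The one balancing step is age-matching, and it applies to the CAD group.

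The quantitative Data Analysis text is the same in Protocol and SAP. Exercise capacity is analysed by a "factorial ANOVA to compare the difference in the levels of improvement between groups", and questionnaires by Wilcoxon tests. No covariate, site term or baseline comparison between hospitals is named, although Protocol Table 1 lists age, sex, BMI and the incremental shuttle walk test (ISWT) at baseline. Both documents close by saying that the results will be used to "draw conclusions about the effectiveness of the treatment options". No limitation for the design is attached.

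**The concern.** Between the two PAD groups, programme type and hospital are one and the same variable. Anything that differs between the hospitals and affects improvement (staff, referral pattern, severity of cases, who drops out) is carried in full by the programme comparison. A significant difference would be read as an effect of mixing PAD with CAD patients when it could be a hospital effect. A null result could equally hide a programme effect that a hospital difference has cancelled.

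This matters because the title and Overview present a feasibility study, while the analysis runs between-group significance tests and the closing sentence claims effectiveness. The caption to Figure 1 likewise promises the overall effectiveness of the intervention.

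**Working it through.** **Inputs from the documents.** One hospital per PAD programme (Recruitment Strategy). 34 recruited per group for 17 completers (Sample size). The inflation reproduces: 17 / (1 − 0.5) = 34, and 3 × 34 = 102 recruited for 3 × 17 = 51 completers. The 17 itself cannot be reproduced, because no effect size, SD, alpha or power is given.

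**Inputs that are assumptions.** The documents give no ISWT variance, pre-post correlation or hospital difference. I take a baseline ISWT imbalance b = 0.5 SD, equal SDs at both times, correlation r = 0.5, 0.7 or 0.8, and no true programme effect.

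**Step 1: can programme and hospital be separated?** For the two PAD groups, write a model with intercept, programme, hospital and baseline. The programme and hospital columns are identical, so the design matrix has rank 3 with 4 columns. Adding covariates does not change this.

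**Step 2: what would a hospital effect do to the test?** Take 17 per group and a two-sided 5% t-test, with a hospital offset in improvement and no programme effect. The test is significant in 8.7% of trials for an offset of 0.2 SD, 13.6% for 0.3 SD and 29.3% for 0.5 SD. If hospital effects are instead random with one hospital per arm, simulation gives a type I error of 6.8% at an intraclass correlation of 0.01, 8.9% at 0.02, 14.9% at 0.05 and 23.9% at 0.10.

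**Step 3: what does a baseline imbalance do to each analysis?** Two situations are possible, and the data cannot tell them apart.

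- *A: at a given baseline, both hospitals have the same 12-week mean.* The adjusted estimate is unbiased. The change score is off by (1 − r)b in baseline SDs. Dividing by the SD of change, √(2(1 − r)), gives b√((1 − r)/2).
- *B: the hospital difference is stable over the 12 weeks.* The change score is unbiased. The adjusted estimate is off by (1 − r)b, in the opposite direction. Dividing by the residual SD, √(1 − r²), gives (1 − r)b/√(1 − r²).

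| r | A: bias of change score (SD of change) | B: bias of adjusted estimate (residual SD) |
|---|---|---|
| 0.5 | 0.25/1.000 = 0.25 | 0.25/0.866 = 0.29 |
| 0.7 | 0.15/0.775 = 0.19 | 0.15/0.714 = 0.21 |
| 0.8 | 0.10/0.632 = 0.16 | 0.10/0.600 = 0.17 |

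In raw units the two estimates always differ by (1 − r)b. A gap between them therefore shows that the baseline imbalance matters, but not which estimate is right.

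**Step 4: scale against noise.** The standard error of a standardised difference at 17 per group is about √(2/17) = 0.34, larger than every bias in the table. Under A, the change-score test is significant in 10.9%, 8.5% and 7.3% of trials for the three correlations, against a nominal 5%.

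**The case against.** The strongest case for the plan has four parts.

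- *The study is a feasibility study, and comparing two existing services is a deliberate choice.* This stands, and lowers the severity. It does not cover significance tests followed by an unrestricted effectiveness conclusion.
- *Case mix is already restricted.* This stands in part. Both PAD groups need a diagnosis within 12 months, no previous PAD intervention, PAD medication or completed exercise programme, no CAD, stroke or heart failure, and the ability to start the ISWT. All groups have the same session length, frequency and duration. But age is unrestricted, no band of PAD severity is set, and half the recruits are expected not to complete, possibly differently at each hospital.
- *Improvement already uses each patient's own baseline.* This is right under situation B and wrong under A. A reader might infer that the change score is the faulty analysis and baseline adjustment the cure. The documents give no basis for preferring either assumption.
- *The biases are small beside the sampling error.* This is true at 17 per group. It would be too strong to say that a baseline difference will be reported as a programme effect; it raises the chance of that.

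Two further inferences are tempting. One is that controls enter by a different route or are existing attenders. The documents state where controls are treated, not how they are approached; they exclude previous completers and assess everyone before the programme starts, and the Figure 2 flowchart is not available here. The other is that age-matching has been spent on the wrong group. Matching the CAD patients takes nothing from the PAD control. Data Analysis says the CAD group will also be compared with the national audit, so the matching may serve the between-group analysis.

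**Conclusion.** The concern holds in a limited form. That programme and hospital cannot be separated follows from the design and needs no numerical assumption. The mismatch between that design and the unrestricted effectiveness conclusion is plain in both documents, as is the absence of any baseline-adjusted estimate.

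The size is not known. Bias of about 0.25 to 0.16 SD of change (change score, situation A) or 0.29 to 0.17 residual SD (adjusted, situation B) rests on an assumed 0.5 SD imbalance and correlations of 0.5 to 0.8. Nothing in the documents shows that such an imbalance exists. Neither analysis alone is decisive. Agreement between them would be reassuring about baseline ISWT imbalance only, because both still contain the whole hospital effect. The documents do not support a claim that the comparison is worthless, or that a different matching scheme is required.

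**What to change.** 1. In the closing statement of the Protocol's Data Analysis and of the SAP, restrict the between-group PAD result, questionnaires included, to a descriptive between-hospital association within a feasibility study. State that programme and site cannot be separated.
2. In the quantitative Data Analysis text of both documents, report the combined minus stand-alone PAD difference in 12-week ISWT adjusted for baseline ISWT, age and sex, beside the unadjusted difference in change. Name the pair as a sensitivity check, and say in advance that disagreement will be reported as uncertainty and not settled in favour of either estimate.
3. Add a table of baseline characteristics by hospital.

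Age-matching of the CAD group can stay, and no frequency-matching of the PAD control is proposed. With only two bands each for age, sex and ISWT there would be 8 cells, or about 34/8 ≈ 4 recruits and 17/8 ≈ 2 completers per cell.

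The cost is wording in two documents, one extra regression and one table from data already collected, and a more modest conclusion.

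### The final accelerometer wear can contain a supervised session that the pre-programme baseline cannot, and no supplied text removes session time from free-living walking

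*Protocol*

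**What the plan says.** Four places in the protocol bear on when the accelerometer is worn.

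- **Inclusion and Exclusion Criteria, General criteria:** "participants will be required to wear an accelerometer on the first week and last week of the 12 week study". This sentence introduces the exclusion for skin conditions.
- **Study Design, Initial Assessment:** "All outcome measures will be taken prior to the patients starting their SEP". The same sentence has them repeated once the programme is complete.
- **Table 1:** "7-day activity monitoring" at baseline and at 12 weeks.
- **Outcome measures, accelerometer item:** for the baseline, "It will remain in place on the leg for a seven-day period, prior to starting the SEP"; for the second wear, "during the last week prior to them completing their SEP". The stated purpose is "to quantify free-living walking", with a reference to a published study that used the device.

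On exposure to supervised exercise, The Programme states: "Patients from all groups will attend a 2 hour supervised exercise session once a week", for 12 weeks. Each session has a warm-up of 10-15 minutes, a conditioning phase of 20-25 minutes and a cool-down of 10 minutes. The PAD exercise list includes treadmill, corridor and trampette walking. On attendance, "Completion will be categorised as attending 8 or more of their 12 sessions".

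The Data Analysis text, the same in protocol and SAP, names a factorial ANOVA for exercise capacity and Wilcoxon tests for questionnaires. It does not mention the accelerometer or the handling of session time.

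**The concern.** The device is meant to show how much patients walk in daily life. Under the Outcome measures timing, the baseline wear precedes the SEP and holds no session, while the final wear lies inside the SEP and can hold one. Walking done under supervision in that session would then enter only the second measurement. It would read as improvement in free-living walking even if daily walking had not changed.

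The final window is also not settled. Initial Assessment points to a measurement after completion, which would contain no session; the Outcome measures section points to the last week before completion, which can. Staff at the two hospitals could follow different sentences. At stake is the within-group change in one secondary-type measure, since the protocol names no primary outcome.

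**Working it through.** There is no stated figure to reproduce; the check is of timing and of session minutes.

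**1. Do the baseline statements conflict?** Twelve sessions, one per week in a fixed slot, have 11 gaps: 11 × 7 = 77 days. Adding a seven-day wear before the first session gives 77 + 7 = 84 days = 12 weeks. On that count the first week in General criteria is the pre-SEP week in Outcome measures. If the SEP itself is taken as 12 full calendar weeks, the pre-SEP wear makes 13 and the two places differ. The wording is loose and allows either reading.

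**2. Can the final wear hold a session?** Assume weekly two-hour sessions in the same slot, at hours 0-2 and 168-170. The gap between them is 168 − 2 = 166 hours. A full 168-hour wear starting at hour s (0 ≤ s ≤ 2) ends at hour 168 + s, so its overlap with session time is (2 − s) + s = 2 hours. A wear of 166 hours placed between the two sessions, or a missed session, avoids overlap. Fitting and removal times are not stated, so overlap is possible but not certain.

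**3. Size for one participant.** Exercise per session: 10 + 20 + 10 = 40 to 15 + 25 + 10 = 50 minutes.

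- All exercise: 40/7 = 5.7 to 50/7 = 7.1 min/day.
- Conditioning phase only: 20/7 = 2.9 to 25/7 = 3.6 min/day.

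The effect on change is the session term in the final wear minus that in the baseline wear:

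| Session in baseline / final wear | Effect on change (min/day) |
|---|---|
| No / no | 0 |
| No / yes | up to +5.7 to +7.1 |
| Yes / yes | about 0; at most (50 − 40)/7 = 1.4 either way |
| Yes / no | down to −5.7 to −7.1 |

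The first two rows apply under the Outcome measures timing. The last two arise only if baseline is worn after sessions have begun.

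**4. Size for a group mean.** Among 17 completers, each one with a session in the final wear adds at most 5.71/17 = 0.34 to 7.14/17 = 0.42 min/day (conditioning only: 2.86/17 = 0.17 to 3.57/17 = 0.21). If all 17 have one, the mean moves by the full 5.7 to 7.1. The completion rule gives no tighter limit, because a completer may miss any four sessions, including the last.

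**5. Relative size.** The documents give no baseline walking time. Purely as an assumption, at 30 min/day one session counted wholly as walking is 40/210 = 19% to 50/210 = 24% of the weekly total; at 120 min/day it is 40/840 = 5% to 50/840 = 6%.

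**The case against.** A reader might infer three stronger things, and the documents do not support them.

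- **That the protocol contradicts itself on the baseline week.** The 84-day count shows that the places can be reconciled, and both sections that set measurement timing put baseline before the SEP. The General criteria sentence explains an eligibility rule. At most it needs rewording.
- **That the final wear must contain a session.** This needs a wear of exactly 168 hours, a fixed weekly slot and attendance. None is guaranteed by the text.
- **That the comparison between the combined and stand-alone PAD groups is biased.** All groups have a weekly session, so the term largely cancels if windows and final-week attendance are alike. A difference of up to 2.9 to 7.1 min/day would need the hospitals to use different windows, which no text suggests.

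It is also fair to say that the minutes are loose limits. Rests, heel raises and sit-to-stands are not walking, which lowers them; other walking during the two-hour visit is not counted, so they are not strict ceilings. CAD exercises are not itemised. Figure 2, the Patient Information Sheet and the cited accelerometer study are not available and may give the timing or the data handling. In a feasibility study with no named primary outcome and no test assigned to these data, the matter is small.

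What stands is that the operative timing is asymmetric, that Initial Assessment and Outcome measures differ on the final wear, and that no supplied text says what happens to session time.

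**Conclusion.** The point holds as a minor, cheap improvement. Following the Outcome measures section as written can add up to about 5.7 to 7.1 min/day to an attending participant's change in free-living walking (2.9 to 3.6 if only the conditioning phase registers), and less to the extent that the exercise is not walking.

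This rests on a pre-SEP baseline, a session falling inside the final wear, and no exclusion rule in the material not seen. It affects within-group change. The PAD comparison is largely protected under matching windows and similar final-week attendance. No percentage can be given without an assumed walking time.

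**What to change.** 1. Reconcile General criteria, Initial Assessment and Outcome measures on one baseline window, the seven days before the first session, and one final window, for all three groups at both hospitals.
2. Log the start and end of any supervised session that falls within a wear, exclude that interval, and express walking per valid wear hour or day.
3. State this in the Outcome measures section and in the SAP's Quantitative data section.

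The cost is wording in both documents, a session-time log at both hospitals and, where a session falls in the final wear, about 2/168 = 1.2% of that record. Fitting the device between the last two sessions (166 of 168 hours) is an alternative only for participants who attend the penultimate session; anyone absent would need a separate fitting visit or would have no final record. Exclusion of logged time is therefore the better main rule.
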